## 5.5 Investigation Content (CRF Form)

### (1) Collect Baseline Information

- 1) The data collected included demographic information such as age, sex, and education level; personal history such as smoking and drinking; medical history such as the presence of other diseases such as hypertension; medication history such as antidiabetic and antihypertensive drugs; and gastrointestinal status and dietary habits.
- 2) Physical examination: General condition, height, weight, blood pressure (BP) including systolic (SBP) and diastolic (DBP), waist circumference (WC), hip circumference (HC), waist-to-hip ratio (WHR), etc.
- 3) The test items included complete blood count, liver and kidney function, HbA1c, TC, TG, HDL-c, LDL-c, FPG, fasting insulin (FIns), and serum uric acid (SUA).

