## **2. Preface**

### **2.1 Research Background and Project Justification**

#### **2.1.1 Epidemiology and Characteristics of Diabetic Nephropathy**

The latest Global Diabetes Atlas, released by the International Diabetes Federation (IDF) in its 10th edition, reveals that approximately 537 million adults worldwide suffered from diabetes mellitus(DM) in 2021. Projections indicate this number will reach 643 million by 2030 and rise to 783 million by 2045 . Diabetic Kidney Disease(DKD), one of the most significant microvascular complications of diabetes, involves chronic kidney damage caused by hyperglycemia. The condition affects the glomeruli, renal tubules, interstitial tissue, and blood vessels, clinically manifesting as persistent albuminuria and/or progressive decline in estimated glomerular filtration rate(eGFR), which may eventually progress to end-stage renal disease(ESRD) . Globally, DKD has become the leading cause of ESRD . The pathophysiological mechanisms of DKD remain complex, with current understanding still requiring further investigation.

The occurrence and development of the disease are related to metabolic disorders, hemodynamic changes and their interaction.

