In recent years, an increasing number of studies have shown that DKD is also an inflammatory reactive disease, in which inflammatory pathways play an important role and may be a key factor leading to the progressive damage of organs. In a hyperglycemic environment, inflammatory cell signaling pathways should be activated, mainly including P38 mitogen-activated protein kinase (MAPK), c-Jun N-terminal kinase (JNK), etc., which in turn activate the NF-κB-related signaling pathway. After activation, NF-κB stimulates the transcription of chemokines, adhesion factors, and pro-inflammatory cytokines, leading to inflammatory cell infiltration in renal tissue and promoting the occurrence and development of DKD [4]. In China, DKD has become the primary cause of end-stage renal disease in middle-aged and elderly patients [5]. Therefore, how to prioritize the prevention, identification, and management of DKD is particularly important. Although renal biopsy is the gold standard for diagnosing DKD, it has not been widely adopted due to its invasive and traumatic nature. Current diagnostic criteria for diabetic kidney disease(DKD) primarily rely on clinical manifestations, including the urine protein-to-creatinine ratio, estimated glomerular filtration rate(eGFR), serum creatinine levels, renal ultrasound findings, and retinopathy presence [6]. However, these indicators demonstrate limited diagnostic sensitivity and specificity for DKD, and fail to effectively assess the severity of renal impairment [7]. **Identifying novel biomarkers to identify high-risk populations with progressive DKD for early intervention could improve patient outcomes, establish dynamic and precise disease progression prediction models, and ultimately enable personalized treatment strategies.**

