### (2) Wear a Continuous Glucose Monitor and Collect Samples

All enrolled subjects were required to wear a continuous glucose monitor (CGM) for 14 days during their first 24-hour hospital stay. Endocrinologists provided personalized dietary guidance based on blood glucose levels, with standardized glucose-lowering regimens. Significant deviations from baseline glucose levels warranted necessary dosage adjustments. Blood glucose variability metrics were collected after 14 days. Additionally, stool and blood samples from all participants were collected and preserved for subsequent analysis.

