#### **5.6 Experimental Scheme**

Step	Period	Filter period	Period of wearing CGM			Follow-up period		
	Study follow-up	Visit 0	Visit 1	Visit 2	Visit 3	Visit 4	Visit 5	Visit 6
	Study date (days)	1 day before enrollment	1 day after enrollment	7 days after enrollment	14 days after enrollment	Within 1 year after enrollment	Within 2 years after enrollment	Within 3 years after enrollment

1	Selection and exclusion criteria	✓						
2	Sign the informed consent form.	✓						
3	Adorn CGM		✓					
4 clinical data	Basic information of the subjects		✓					
	Clinical diagnosis		✓					
	Personal history		✓					
	History of past illness		✓					
	Check-up		✓					
5 clinical examination Inspection	Routine blood test			✓				
	Liver function			✓				
	Renal function			✓				
	HbA1c			✓				
	Blood fat			✓				
	Fasting insulin (FIns)			✓				
	Blood sugar			✓				
	Thyroid function			✓				
	Coagulation function			✓				
6	Medication during CGM monitoring				✓			
7	Fecal collection		✓					
8	Blood collection		✓					
9	Medications taken after discharge				✓			

10	Download the CGM report				✓			
11	Fecal microbiota sequencing					✓		
12	Metabolite assay in serum					✓		
13	Progression events of DKD during follow-up					✓	✓	✓
14	Assessment of MACE events during follow-up					✓	✓	✓
15	Death events during follow-up		✓	✓	✓	✓	✓	✓
16	Adverse event monitoring		✓	✓	✓			
17	Deviation from plan record		✓	✓	✓	✓	✓	✓
18	Fill in CRF		✓	✓	✓	✓	✓	✓

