## 5.7 Collection, Storage, Use, and Destruction of Research Data and / or Biological Samples

### 5.7.1 STUDY DATA

**Data Collection:** This study will collect participants' age, gender, education level, medical history, medication history, and physical measurements including height, weight, blood pressure (BP) (systolic [SBP] and diastolic [DBP]), waist circumference (WC), hip circumference (HC), and waist-to-hip ratio (WHR) through face-to-face interviews, physical examinations, and continuous glucose monitoring (CGM) tests. The CGM will also collect real-time blood glucose data.

**Storage:** The above information is stored in the medical information platform of our hospital.

**Use:** All data collected in this study are used for clinical research data analysis and will not be used for commercial purposes.

**Destruction:** The study will be destroyed in accordance with the regulations 5 years after the study is completed.

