### 5.7.2 Biological Specimen

**DATA COLLECTION:** Blood and stool samples were collected from the participants and analyzed for complete blood count, liver function, kidney function, glycated hemoglobin, blood lipids, fasting insulin, thyroid function, coagulation function, and gut microbiota.

**Storage:** All the specimens were stored in the biological sample bank of our hospital.

**Use:** All data collected in this study are used for clinical research data analysis and will not be used for commercial purposes

road .

Destruction: The study will be destroyed in accordance with the regulations 5 years after the study is completed.

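### No urine albumin or protein value is recorded at baseline, so albuminuria cannot be adjusted for or offered to the prediction model

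*Protocol*

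**What the plan says.** The background in Section 2.1.1 describes DKD as "clinically manifesting as persistent albuminuria and/or progressive decline in estimated glomerular filtration rate(eGFR"). It then lists the clinical indicators on which diagnosis currently relies, "including the urine protein-to-creatinine ratio, estimated glomerular filtration rate(eGFR), serum creatinine levels" among them, with the urine measure named first. Inclusion criterion 2 (Section 5.3.2) requires a diagnosis by an external guideline and does not restate its thresholds.

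The baseline test items in Section 5.5 (1) begin "The test items included complete blood count, liver and kidney function, HbA1c" and run on as "HbA1c, TC, TG, HDL-c, LDL-c, FPG, fasting insulin (FIns), and serum uric acid (SUA"). For the CGM period, Section 5.5 (2) says that "stool and blood samples from all participants were collected and preserved for subsequent analysis". In the Section 5.6 schedule, the block headed "5 clinical examination Inspection" has rows for blood tests, renal function included, and none for urine. Section 5.7.1 obtains the study data "through face-to-face interviews, physical examinations, and continuous glucose monitoring (CGM) tests". Section 5.7.2 reads "Blood and stool samples were collected from the participants and analyzed for complete blood count, liver function, kidney function", and names no third specimen.

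The primary end point in Sections 3.1 and 5.5 (3) is renal failure or a sustained 30% fall in eGFR. Section 5.8.2 gives age, sex, disease duration and baseline glucose as examples of confounders. The prediction model draws on clinical indicators (Sections 3.2.1 and 4.1.4) and baseline data (Section 5.8.2), together with the omics and inflammatory measures.

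**The concern.** The study asks whether GV, gut microbiota and serum metabolites carry prognostic information about DKD progression. The severity of existing kidney damage plausibly relates to all of these and to the end point. The protocol's own background points that way: Section 2.1.2 cites work linking time in range to progression of proteinuria, and Section 2.1.3 links dysbiosis to renal function.

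By the protocol's own description, renal severity has two faces, filtration and albuminuria. The plan records the first and has no place for the second. A marker that only stands in for albuminuria could then be selected as prognostic, or as a mediator, with nothing in the data set to expose it. Nor could anyone show that the omics model improves on a urine protein value.

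Unlike the choice of covariates, this cannot be left to an analysis plan. A baseline value not captured around enrollment may not be recoverable after three years of follow-up.

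**Working it through.** **Step 1. Is a urine value collected anywhere?**

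| Protocol section | What it lists | Urine albumin or protein |
|---|---|---|
| 5.5 (1) test items | blood count, liver and kidney function, HbA1c, lipids, fasting glucose, insulin, uric acid | no |
| 5.5 (2) samples | stool, blood | no |
| 5.6 schedule | blood tests including renal function, thyroid, coagulation | no |
| 5.7.1 study data | demographics, history, physical measurements, CGM | no |
| 5.7.2 specimens | blood, stool | no |

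The result is 0 of 5. The test list in 5.5 (1) is closed, whereas the physical-examination list just before it ends in an et cetera. Section 5.7.2 places kidney function among the tests on blood and stool, so the term gives no support for reading a urine test into it.

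**Step 2. Is it named as a model input?** Sections 3.2.1, 4.1.4 and 5.5 (5) and the two relevant parts of 5.8.2 (regression adjustment; model data) do not mention it: 0 of 5. Some of these lists are open-ended, but they can draw only on what Step 1 collects. The same limit applies to the propensity score matching in 5.8.2.

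**Step 3. What is available for renal severity?** Kidney function is collected at baseline, and the end point needs a baseline eGFR. So eGFR can serve as covariate and predictor, although it is not among the example confounders. Only the urinary component is out of reach.

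**Step 4. How large could the bias be?** The plan states no figure on this, and the documents give neither the risk ratio for albuminuria nor its prevalence by GV group. What follows is illustration from assumed inputs.

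Let RR be the risk ratio of progression for raised albuminuria, p_high and p_low its prevalence in the high- and low-GV groups, and let GV have no true effect. The spurious risk ratio for high GV is

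(1 + (RR − 1) × p_high) / (1 + (RR − 1) × p_low)

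| RR | p_high | p_low | Calculation | Factor |
|---|---|---|---|---|
| 2 | 0.9 | 0.8 | 1.9 / 1.8 | 1.06 |
| 4 | 0.9 | 0.8 | 3.7 / 3.4 | 1.09 |
| 2 | 0.4 | 0.3 | 1.4 / 1.3 | 1.08 |
| 3 | 0.5 | 0.3 | 2.0 / 1.6 | 1.25 |
| 4 | 0.6 | 0.3 | 2.8 / 1.9 | 1.47 |

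The first two rows suit a cohort in which most patients have albuminuria; the others suit one in which a minority of the low-GV group does. The range is 1.06 to 1.47, and it is for an unadjusted ratio. Adjusting for eGFR would remove some of it, by an amount that cannot be computed here.

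**Step 5. Room in the model.** Section 5.4 plans for at least 30 events (975/156 × 30 = 187.5 patients before dropout). One or two further parameters are a real cost against 30 events, but a small one beside the number of omics features to be screened.

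**The case against.** The strongest reply is that renal severity is not ignored. Kidney function is tested at baseline and clinical indicators are eligible for the model. The confounders in Section 5.8.2 are introduced as examples, and a full covariate list commonly belongs in the analysis plan. This stands. A reader might infer that baseline kidney damage as a whole goes unadjusted and cannot be a predictor; the documents do not support that, because nothing excludes eGFR. The reply does not reach albuminuria, since an analysis plan cannot use a value that was never recorded.

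A second reply is that albuminuria does not by itself define DKD. That also stands. Section 2.1.1 says and/or, so some patients may qualify on eGFR alone, and the diagnostic indicator it names is urine protein rather than albumin. Nor does the protocol say which test qualified each patient. That a urine value is on file for everyone is therefore an inference, made likelier by the exclusion of nephrotic syndrome but not established.

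Third, the size of the bias rests wholly on assumption. At high prevalence in both groups it falls to 1.06 to 1.09, and excluding nephrotic syndrome removes the heaviest proteinuria and may narrow it further. This is accepted.

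Fourth, if glycemia drives proteinuria, as the work cited in Section 2.1.2 may suggest, albuminuria may lie on the path from GV to renal outcome. Adjusting for it could then remove part of the effect under study. This is a good point, and it shapes the fix.

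**Conclusion.** The omission is real, and narrower than it may first look. No list of data, samples or specimens contains a urine albumin or protein value, although the protocol treats albuminuria as one of two main manifestations of the disease. As written, albuminuria cannot be adjusted for or offered to the model, and a marker that merely tracks it could be reported as prognostic.

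The possible inflation of an unadjusted risk ratio is about 1.06 to 1.47, assuming risk ratios of 2 to 4 and prevalence differences of 10 to 30 points. This shows what could happen; it is not an estimate for this cohort.

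A reader might also conclude that no added value over routine clinical data can be shown. That goes too far: blood pressure, HbA1c, lipids, uric acid and kidney function are all collected, and added value over those can be tested. What cannot be tested is added value over urine protein. The point merits correction because it is cheap to fix now and may be impossible to fix later.

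**What to change.** Add one baseline field to the CRF for the urine albumin- (or protein-) to-creatinine ratio, with the type of ratio recorded. Transcribe it from the diagnostic work-up where it is on file and record it as missing otherwise. Carry the item into Sections 5.5 (1), 5.6 and 5.7.1 so that the lists agree.

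In Section 5.8.2, name baseline eGFR and the log-transformed ratio as adjustment covariates in the Cox and MaAsLin prognosis analyses. In Section 5.5 (5), name both as clinical candidate predictors. For the Cox analysis of GV against outcome and for the mediation analysis, report results with and without the urine ratio, because it may lie on the pathway.

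The cost is one extra field, some missing values in a share of patients that the documents do not reveal, and one or two more parameters against about 30 planned events.

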### (2) Wear a Continuous Glucose Monitor and Collect Samples

All enrolled subjects were required to wear a continuous glucose monitor (CGM) for 14 days during their first 24-hour hospital stay. Endocrinologists provided personalized dietary guidance based on blood glucose levels, with standardized glucose-lowering regimens. Significant deviations from baseline glucose levels warranted necessary dosage adjustments. Blood glucose variability metrics were collected after 14 days. Additionally, stool and blood samples from all participants were collected and preserved for subsequent analysis.

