## **III. RESEARCH OBJECTIVES**

**3.1 Main objective:** To explore the relationship between glycemic variability, gut microbiota metabolites and prognosis of patients with DKD.

**(1) Study subjects:** patients with diabetic nephropathy.

**(2) Exposed factors:** glycemic variability (assessed by continuous glucose monitoring CGM); gut microbiota, serum metabolites (assessed by 16S rRNA high-throughput sequencing technology and serum non-targeted liquid chromatography-mass spectrometry LC-MS) and inflammatory factors.

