#### 4.1.1 Assessing the impact of glycemic variability on prognosis in patients with diabetic kidney disease

- (1) in prospective cohort studies, patients with DKD were enrolled, and their blood glucose was monitored with a continuous glucose monitor for 14 days, followed by longitudinal follow @-@ up to record adverse prognostic events.
- (2) The relationship between glycemic variability and prognosis was analyzed, and the optimal TIR control target for DKD patients was discussed.

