#### 4.1.3. Gut Microbiota and Serum Metabolites in DKD Patients with Different Blood Glucose Variability Groups and Their Correlation with Prognosis

(1) Patients with DKD were divided into high GV group and low GV group according to GV status, and the intestinal microbiota characteristics and serum metabolites characteristics of patients in different GV groups were analyzed.

(2) Based on the association between gut microbiota, serum metabolic biomarkers and prognosis, the relationship between the bacterial co-abundance group (CAG) and the functional modules of serum metabolites was further established to explore their correlation with glycemic variability and poor prognosis.

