#### 1) Inclusion Criteria:

- ① Age 18-65 years;
- ② The diagnosis of DKD meets the relevant criteria in the "China Diabetes Nephropathy Prevention and Treatment Guidelines (2021 Edition)";
- ③ Type 2 diabetes mellitus, treated with insulin analogues or oral antidiabetic drugs, diagnosed according to the 1999 WHO criteria;
- ④ no changes in the antidiabetic regimen were made for at least 3 months before enrollment.
- ⑤ informed consent was obtained voluntarily.

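### Glycemic variability is measured over 14 days in which diet and dose may be changed in response to glucose, so the exposure is partly variability under in-study treatment

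*Protocol*

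**What the plan says.** Section 3.1 of the protocol names GV measured by CGM as an exposure of the main objective, beside gut microbiota, serum metabolites and inflammatory factors. Section 4.1.1 sets the measurement: "their blood glucose was monitored with a continuous glucose monitor for 14 days". Section 4.1.3 uses the result to form groups: "Patients with DKD were divided into high GV group and low GV group according to GV status". Section 5.5 (4) adds an intermediate group.

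Section 5.5 (2) describes what happens around the monitoring. Diet and treatment come first: "Endocrinologists provided personalized dietary guidance based on blood glucose levels, with standardized glucose-lowering regimens". Then dose: "Significant deviations from baseline glucose levels warranted necessary dosage adjustments". The next sentence gives the read-out: "Blood glucose variability metrics were collected after 14 days".

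The only stability requirement is an inclusion criterion in section 5.3.2: "no changes in the antidiabetic regimen were made for at least 3 months before enrollment". The schedule in section 5.6 lists "Medication during CGM monitoring" at Visit 3 (day 14). Section 5.8.2 names age, sex, disease duration and baseline glucose as examples of confounders and does not mention treatment during monitoring. Sections 2.2.1 and 2.2.3 present smaller glucose fluctuations and individual treatment plans as benefits of taking part.

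**The concern.** The exposure is meant to describe the patient. If diet advice and dose respond to glucose while it is being recorded, the 14-day figure combines the patient's own variability with the response to management. Dose changes are triggered by glucose deviation, so they fall on selected patients rather than at random.

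Four uses of GV inherit this: its relation to prognosis, the optimal control target in section 3.1 (4), the comparison of microbiota and metabolites across GV groups, and the mediation analysis in section 5.8.2. The target is the most exposed. A threshold estimated from variability that was being managed during measurement does not translate directly into a statement about patients' usual variability.

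**Working it through.** The plan gives no figure on this point, so the check is mainly a comparison of sections.

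1. **Window.** Sections 4.1.1 and 5.6: CGM is fitted at Visit 1 and the report is downloaded at Visit 3, day 14.
2. **Treatment in the window.** Section 5.5 (2) places glucose-based diet guidance, standardized regimens and dose adjustment in the CGM paragraph, between fitting the device and collecting the metrics. No run-in, masking of CGM values or pre-adjustment segment is described.
3. **Stability.** The criterion in section 5.3.2 covers the 3 months before enrollment. Nothing extends it into the window.
4. **Setting.** Recruitment is from inpatients (section 5.3.1), and post-discharge medication is also recorded at Visit 3. This suggests that some windows span hospital and home, but the protocol does not say so.
5. **Records.** Medication during CGM is recorded once, at Visit 3. The schedule does not say that dates of change are captured.
6. **Which analyses use GV.** The four named above do. Screening microbiota, metabolites and inflammatory factors against prognosis (sections 3.1 (4) and 4.1.2) does not. Nor does the sample size in section 5.4, which is built on outcome groups.

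**Illustration only, on assumptions that are not in the protocol.** Let s be the share of measured GV variance that comes from in-window treatment unrelated to the patient's own GV. Suppose groups are split at the median, and suppose a true hazard ratio of 2.0 per SD of own GV.

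- Correlation of measured with own GV = √(1 − s).
- Share placed in the wrong group = arccos(√(1 − s))/π.
- Attenuated hazard ratio, approximately = 2.0^(1 − s).

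| s | Wrong group | Of 210 in the modeling cohort | Hazard ratio |
|---|---|---|---|
| 0.10 | 10% | about 22 | 2.0^0.9 = 1.87 |
| 0.30 | 18% | about 39 | 2.0^0.7 = 1.62 |
| 0.50 | 25% | about 52 | 2.0^0.5 = 1.41 |

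The table shows how sensitive the analysis would be to random contamination. It does not estimate the bias here: s is unknown, the protocol gives no cut-point, and treatment triggered by glucose is not random error.

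**The case against.** The best defence is that this may be ordinary inpatient care in an endocrinology department, that standardized regimens may be intended to reduce differences between patients, and that the study records medication during monitoring. The covariate list in section 5.8.2 is open-ended, and a statistical analysis plan not shown here could use that record. Much of this stands. The absence of a medication covariate is not in itself a fault of the protocol. But ordinary care changes measured GV just as study-driven care does. A later analysis plan also cannot recover dates of change that were never recorded.

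Some stronger readings are tempting, and the protocol does not support them:

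- **That the inclusion criterion and section 5.5 (2) contradict each other.** One covers the time before enrollment and the other the time after, so both can hold.
- **That stable patients are moved to a new regimen and so appear variable.** No switch is stated, and dose changes are tied to significant deviations.
- **That every main analysis is compromised.** Biomarker screening against prognosis does not use GV.
- **That the contrast between GV groups is compressed.** Adjustment could lower GV in unstable patients, or add a step change that raises it.
- **That a known fraction of patients is misclassified.** Any such percentage comes from an assumed random-error model.

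**Conclusion.** The point holds in a limited form. With the protocol followed as written, the 14-day metric is partly GV under in-study treatment, and the protocol neither says so nor provides a way to separate the two. This qualifies the GV-prognosis association, the GV control target, the group comparisons and the mediation analysis. Size and direction cannot be determined from the protocol. The conclusion rests on reading section 5.5 (2) as describing care during the monitoring window, which its order and placement support. It does not depend on whether that care is study-driven or routine. This is an inexpensive improvement that should be made, not a flaw that invalidates the study.

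**What to change.** None of these changes alters a clinical rule.

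1. In section 5.5 (2), state whether treatment is held or may change during monitoring.
2. On the Visit 3 medication record, capture the dates of each dose or regimen change, of diet guidance and of discharge. This has to be in place while patients are being monitored.
3. Keep the 14-day metric, but describe it as GV under in-study treatment and word the GV-target conclusion in those terms.
4. In section 5.8.2, pre-specify two sensitivity analyses: (a) GV from CGM days before the first dated change, subject to a stated minimum wear time; (b) the full 14-day GV, restricted to patients with no change.
5. Show adjustment for in-window regimen change only as a further sensitivity analysis. Change is triggered by glucose deviation, so it may be a consequence of GV, and adjusting for it could remove real signal.

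Cutting at the first change is safer than taking each patient's longest constant segment, which may lie entirely after a change.

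The cost is a few more dates to record, and shorter, less precise GV records in adjusted patients. Analysis (b) covers a selected, probably more stable subgroup. If diet guidance or a standardized regimen begins for everyone on day 1, neither analysis can remove that part. They then isolate only later changes, and the report should say so.
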